# 6.2.2. Day 1 Assessments

The following evaluations are to be completed at the Day 1 Visit. The Investigator must have confirmed eligibility before proceeding with the Day 1 visit. The subject must complete all study procedures before being administered the study drug:

- Short Form 36 Health Survey (SF-36), HIV Symptoms Distress Module, Work Productivity and Activity Impairment Questionnaire (WPAI) and Pittsburgh Sleep Quality Index (PSQI) to be completed by the subject. Subject is to read questionnaire by himself/herself and write/mark answers directly onto questionnaires.
- Review of AEs and changes in concomitant medications
- Complete physical examination (urogenital/anorectal exams will be performed at the discretion of the Investigator)
- Vital signs measurement (blood pressure, pulse, respiration rate, and temperature), including weight
- Obtain blood and urine samples as described in Sections 6.10.1 and 6.10.2.
- Dispense study drug
- Observed first dose administration of the assigned study drugs as described in Section 5.3
- Subjects should be instructed to take study drugs without regard to food. The subject should be counseled regarding the importance of adherence and taking their study medications at approximately the same time each day as directed by the Investigator.

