## 6.10.1. Blood Samples

- Blood sample collection for the following laboratory analyses:
  - Serum pregnancy test (females of childbearing potential only). If the test is positive, the subject will not be enrolled
  - Chemistry profile: alkaline phosphatase, AST, ALT, total bilirubin, direct and indirect bilirubin, total protein, albumin, CPK, bicarbonate, blood urea nitrogen (BUN), chloride, creatinine, glucose, potassium, sodium, amylase (reflex lipase testing is performed in subjects with total amylase > 1.5 × ULN)
    - Calcium, phosphorus, magnesium (Screening and Day 1)

- Metabolic assessments: Fasting (no food or drinks, except water, at least 8 hours prior to blood collection) glucose and lipid panel (total cholesterol, HDL, direct LDL, and triglycerides) collected at Day 1, Weeks 12, 24, and 48, and every 24 weeks thereafter, End of Blinded Treatment Visit, and every 24 weeks in the OL extension phase
  - If the subject has not fasted prior to the visit, the visit may proceed, but the subject must return within 72 hours in a fasted state to draw blood for the metabolic assessments
- eGFR according to the Cockcroft-Gault formula:

Male: 
$$\frac{(140 - \text{age in years}) \times (\text{wt in kg})}{72 \times (\text{serum creatinine in mg/dL})} = \text{creatinine clearance (CLcr) (mL/min)}$$

$$\frac{(140 - \text{age in years}) \times (\text{wt in kg})}{72 \times (\text{serum creatinine in umol/L}) \times 0.6786} = \text{CLcr (mL/sec)}$$
Female: 
$$\frac{(140 - \text{age in years}) \times (\text{wt in kg})}{72 \times (\text{serum creatinine in mg/dL})} \times 0.85 = \text{CLcr (mL/min)}$$

$$\frac{(140 - \text{age in years}) \times (\text{wt in kg})}{72 \times (\text{serum creatinine in umol/L}) \times 0.6786}$$

- Hematology profile: complete blood count (CBC) with differential and platelet count
- CD4+ cell count and percentage
- Plasma HIV-1 RNA
- HBV blood panel (Screening, Week 48, every 48 weeks through End of Blinded Treatment Visit, and Weeks 48OL, 96OL): Hepatitis B virus surface antigen (HBsAg), Hepatitis B virus surface antibody (HBsAb) and Hepatitis B virus core antibody (HBsAb)

The following tests will be conducted by the central laboratory if the following criteria are met:

- If positive HBsAg: reflex testing for plasma HBV DNA, Hepatitis B virus e-antigen (HBeAg) (if negative, reflex Hepatitis B virus e-Antibody [HBeAb]), and quantitative HBsAg

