- o. Chemistry profile: alkaline phosphatase, AST, ALT, total bilirubin, direct and indirect bilirubin, total protein, albumin, CPK, bicarbonate, BUN, calcium, chloride, creatinine, glucose, phosphorus, magnesium, potassium, sodium, and amylase (reflex lipase testing is performed in subjects with total amylase > 1.5 × ULN). After Day 1, calcium, phosphorous, and magnesium will not be collected. Analyses of glucose will be done as part of the fasting metabolic assessments, and not as part of the chemistry profile at Day 1, Weeks 12, 24, 48, post Week 48 (every 24 weeks), and End of Blinded Treatment, Week 24OL, Week 48OL, Week 96OL.
- p. CBC with differential and platelet count.
- q. Fasting (no food or drinks, except water, at least 8 hours prior to blood collection) glucose and lipid panel (total cholesterol, HDL, direct LDL, triglycerides). If the subject has not fasted prior to the visit, the visit may proceed, but the subject must return within 72 hours in a fasted state to draw blood for the metabolic assessments.
- r. Metabolic assessments during the post Week 48 will be done every 24 weeks.
- s. Hepatitis C virus serology. Subjects who are HCVAb positive will have a HCV RNA test performed.
- t. HBV blood panel will be performed at Screening, Week 48, every 48 weeks through End of Blinded Treatment Visit, and Weeks 48OL, 96OL: HBsAg, HBsAb, HBcAb

CONFIDENTIAL Page 90 28 June 2018

- u. **For subjects who are HBV co-infected at any visit:** The following HBV Blood panel will be conducted by the central laboratory: HBsAb, HBsAg (qualitative and quantitative), and HBeAg (if negative, reflex HBeAb)
  - For subjects who are NOT HBV co-infected at any visit: The following HBV Blood panel will be conducted by the central laboratory: HBsAb, HBcAb, and HBsAg. Subjects who are HBsAg or HBcAb positive will have a reflex test for HBV DNA (viral load)
- v. For subjects who are HBV co-infected at any visit: Plasma HBV DNA at every visit (including OL extension period [not collected at Screening and 30-day Follow-up])
- w. Randomization may be performed up to 3 days prior to the in-clinic Day 1 visit provided that all screening procedures have been completed and subject eligibility has been confirmed.
- x. Initiation of the first dose of study drug is to take place in-clinic following completion of study procedures at the Day 1 visit.
- y. Open label study drug, B/F/TAF FDC will be dispensed to subjects participating in the OL extension for up to 96 weeks.

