# Study Day 1 for the all B/F/TAF analysis is defined as

- For subjects who actually received B/F/TAF in the randomized phase of this study (ie, B/F/TAF group), **Study Day 1** for the all B/F/TAF analysis is defined as the day when the first dose of B/F/TAF in the randomized phase was taken, as recorded on the Study Drug Administration eCRF form.
- For subjects who actually received DTG + F/TAF in the randomized phase of this study and then receive at least 1 dose of B/F/TAF in the extension phase (ie, DTG + F/TAF to B/F/TAF group), **Study Day 1** for the all B/F/TAF analysis is defined as the day when the first dose of B/F/TAF in the extension phase was taken (ie, OL B/F/TAF), as recorded on the Study Drug Administration eCRF form.

Last Dose Date for the All B/F/TAF Analysis is the latest of B/F/TAF (including both randomized phase and open label phase) end dates recorded on the Study Drug Administration eCRF form.

If the last dose date for the all B/F/TAF analysis is missing (eg, only year of last dose date is known or completely missing due to lost to follow-up), the latest of the B/F/TAF (including both randomized phase and open label phase) start dates and end dates, the latest clinical and laboratory visit dates, excluding the 30-day follow-up visit date, will be used to impute the last dose date.

**Study Days** are calculated relative to Study Day 1 for the randomized phase analysis. For events that occurred on or after the Study Day 1 date, study days are calculated as (visit date minus Study Day 1 plus 1). For events that occurred prior to Study Day 1 for either analysis, study days are calculated as (visit date minus Study Day 1).

**Last Study Date** is the latest of the study drug (including DTG + F/TAF, and B/F/TAF in both randomized phase and open label phase) start dates and end dates, the clinic visit dates, and the laboratory visit dates, including the 30-day follow-up visit date.

**Baseline Value** is defined as the last nonmissing value obtained on or prior to Study Day 1 for the randomized phase analysis or the all B/F/TAF analysis, as appropriate. Subjects who actually received DTG + F/TAF in the randomized phase and received at least 1 dose of B/F/TAF in extension phase will have a baseline for Randomized Phase Analysis and a new baseline value for the all B/F/TAF analysis.

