The analysis windows for metabolic assessments (including fasting glucose and lipid panel: total cholesterol, high density lipoprotein [HDL], direct low density lipoprotein [LDL], triglycerides, and total cholesterol to HDL ratio) are presented in Table 4 and Table 5 for randomized phase analysis and all B/F/TAF analysis separately.

Table 4. Analysis Windows for Metabolic Assessments for Randomized Phase Analysis

Visit ID	Nominal Day	Lower Limit	Upper Limit
Baseline			1
Week 12	84	2	126
Week 24	168	127	252
Week 48	336	253	420
Week 72	504	421	588
Week K	K*7	(K-12)*7+1	(K+12)*7

Note: Week K is every 24 weeks after previous visit.

Table5. Analysis Windows for Metabolic Assessments for all B/F/TAF Analysis

	B/F/TAF Group			DTG + F/TAF to B/F/TAF		
Visit ID	Nominal Day	Lower Limit	Upper Limit	Nominal Day	Lower Limit	Upper Limit
Baseline			1			1
Week 12	84	2	126	NA	NA	NA
Week 24	168	127	252	168	2	252
Week 48	336	253	420	336	253	420
Week 72	504	421	588	504	421	588
Week 96	672	589	756	672	589	756
Week K	K*7	(K-12)*7+1	(K+12)*7	K*7	(K-12)*7+1	(K+12)*7

NA = Not applicable

Note: For the B/F/TAF group, Study Day 1 is the first dose date of the B/F/TAF received in the randomized phase; For the DTG + F/TAF to B/F/TAF group, Study Day 1 is the first dose date of the B/F/TAF received in the extension phase.

Note: Week K is every 24 weeks after previous visit.

The analysis windows for HBV Serology (including HBsAb, HBsAg, hepatitis B e-antigen [HBeAg], hepatitis B e-antibody [HBeAb], HBcAb) and HCV Serology (including HCV antibody [HCVAb]), and HCV RNA assessments are presented in Table 6 and Table 7.

Table 6. Analysis Windows for HBV and HCV Serology and HCV RNA Assessments for Randomized Phase Analysis

Visit ID	Nominal Day	Lower Limit	Upper Limit
Baseline			1
Week 48	336	2	504
Week K	K*7	(K-24)*7+1	(K+24)*7

Note: Week K is every 48 weeks after previous visit.

Table 7. Analysis Windows for HBV and HCV Serology, and HCV RNA Assessments for all B/F/TAF Analysis

	B/F/TAF Group			DTG	+ F/TAF to B/F/	/TAF
Visit ID	Nominal Day Lower Limit U		Upper Limit	Nominal Day	Lower Limit	Upper Limit
Baseline			1			1
Week 48	336	2	504	336	2	504
Week 96	672	505	840	672	505	840
Week K	K*7	(K-24)*7+1	(K+24)*7	K*7	(K-24)*7+1	(K+24)*7

NA = Not applicable

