#### 7.2.2.1. Treatment-Emergent Laboratory Abnormalities

Treatment-emergent laboratory abnormalities are defined as values that increase at least 1 toxicity grade from baseline at any postbaseline time point, up to 30 days after permanent discontinuation of study drug. If the relevant baseline laboratory value is missing, any abnormality of at least Grade 1 observed within the time frame specified above will be considered treatment emergent.

Fasting glucose and nonfasting glucose (including glucose results without a known fasting status) are graded based on different grading scales as specified in the protocol. Treatment-emergent laboratory abnormalities will be summarized for fasting glucose. Maximum postbaseline grade, instead of treatment-emergent grade, for nonfasting glucose (including glucose results without a known fasting status) will be summarized, as nonfasting glucose was not assessed at baseline visit for most of the subjects; therefore, an abnormality is treatment-emergent or not cannot be determined for these subjects.

Both urine red blood cell (RBC) based on microscopic examination, labeled as Hematuria (Quantitative), and urine blood based on a dipstick, labeled as Hematuria (Dipstick), are assessed and assigned a toxicity grade in this study. Hematuria (Quantitative) is a reflex test. Urine RBC based on microscopic examination or dipstick will be presented in laboratory toxicity summary tables and listings.

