## 7.2.3. Metabolic Laboratory Evaluations

For metabolic assessments, including fasting glucose and the lipid panel (ie, total cholesterol, triglycerides, LDL, HDL, total cholesterol to HDL ratio), only those measurements under fasting status will be summarized based on the Safety Analysis Set for randomized phase analysis and All B/F/TAF Analysis Set for all B/F/TAF analysis, respectively. P-values comparing the difference between the 2 treatment groups in baseline values and the change from baseline in metabolic assessment will be estimated from a 2-sided Wilcoxon rank sum test for randomized phase analysis. No formal statistical testing is planned for all B/F/TAF analysis.

For randomized phase analysis, the number and percentage of subjects who took lipid modifying medications at study entry and initiated the medications during the randomized phase of study will be provided by treatment group based on the Safety Analysis Set. Statistical comparisons of the subject incidence rates between the 2 treatment groups will be performed using Fisher's exact test. For all B/F/TAF analysis, the number and percentage of subjects who took lipid modifying medications at the First Dose of B/F/TAF and While Receiving B/F/TAF will be provided by treatment group based on the All B/F/TAF Analysis Set. No formal statistical testing is planned for all B/F/TAF analysis.

A lipid modifying medication is defined as a medication with drug class (based on the World Health Organization [WHO] Drug ATC2 term) = "LIPID MODIFYING AGENTS" and WHO Drug preferred drug name containing the wording of "STATIN".

For randomized phase analysis, a sensitivity analysis of fasting lipid tests will be performed by excluding subjects who took lipid modifying medications at study entry or initiated the medications during the study: baseline values, Week 48 values, and changes from baseline at Week 48 will be summarized by treatment group using descriptive statistics for randomized phase analysis. Baseline and change from baseline at Week 48 will be compared between the 2 treatment groups using a 2-sided Wilcoxon rank sum test for randomized phase analysis. Only subjects with both baseline and Week 48 postbaseline values will be included in the analysis.

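### Conflicting Day 1 rules can leave a dosed subject without a fasting baseline, and the SAP then counts pre-existing lipid or glucose grades as treatment-emergent

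*Protocol*

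**What the plan says.** **Timing of the fasting draw.** Protocol 6.10.1 makes Day 1 the first visit with fasting glucose and lipids. For a subject who has not fasted, "the visit may proceed, but the subject must return within 72 hours in a fasted state to draw blood". Footnote q of Appendix 2 repeats this, and neither place exempts Day 1. The procedures table has no metabolic panel at Screening.

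**Timing of the first dose.** Protocol 6.2.2, which lists the 6.10.1 blood samples among the Day 1 evaluations, states: "The subject must complete all study procedures before being administered the study drug". Footnote x of Appendix 2 agrees: "Initiation of the first dose of study drug is to take place in-clinic following completion of study procedures at the Day 1 visit".

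**Baseline and windows.** SAP 3.8.1 sets Study Day 1 as the day of the first blinded dose; baseline is "defined as the last nonmissing value obtained on or prior to Study Day 1". In SAP 3.8.2, the table headed "Table 4. Analysis Windows for Metabolic Assessments for Randomized Phase Analysis" closes baseline at Day 1 and runs Week 12 from Day 2 to Day 126.

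**Fasting status and grading.** SAP 7.2.2 leaves nonfasting lipids ungraded. SAP 7.2.3 says that for the metabolic tests "only those measurements under fasting status will be summarized". SAP 7.2.2.1 adds a fallback: "If the relevant baseline laboratory value is missing, any abnormality of at least Grade 1 observed" up to 30 days after study drug ends is treatment-emergent. Protocol 8.6.3 has the same fallback, and Protocol 8.3 likewise treats a missing pre-treatment result as normal. SAP Appendix 8 item 13a grades every post-baseline result, not only those chosen for by-visit tables.

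**The concern.** The protocol creates a make-up fasting sample, but the SAP has no rule for one that belongs to Day 1. If the subject has already been dosed, the sample meant to supply baseline is classed as on-treatment, and the missing-baseline fallback then applies to the sample itself and to every later fasting value. A subject who entered with raised LDL or cholesterol would appear in the safety tables as having developed it on study drug.

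Two outputs are exposed, in different ways:

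- The treatment-emergent laboratory tables could be inflated by abnormalities that pre-date dosing.
- The change-from-baseline analyses of fasting metabolic tests would lose subjects. SAP 7.2.3 reports between-arm p-values for these overall and within the F/TAF and F/TDF backbone subgroups. Its sensitivity analysis excluding users of lipid-modifying drugs needs both a baseline and a Week 48 value.

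Safety and tolerability is the study's only secondary objective, so these tables matter, although they do not decide the trial.

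**Working it through.** The plan states no figure on this point, so there is none to reproduce. The check has three parts.

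**1. Where a make-up sample lands.** Assume the first dose is given at the unfasted Day 1 visit. Under SAP 3.8.1, Study Day = visit date − Study Day 1 + 1.

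| Calendar days after dosing | Study Day | Table 4 window | Days before nominal Day 84 |
|---|---|---|---|
| 0 | 1 | Baseline | – |
| 1 | 2 | Week 12 | 82 |
| 2 | 3 | Week 12 | 81 |
| 3 | 4 | Week 12 | 80 |

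Only a same-day fasting draw still counts as baseline. SAP 3.8.3 picks the record nearest the nominal day. Any later fasting sample in the window is at most 79 days before Day 84 (Day 5) or 42 days after it (Day 126), so it displaces a Day 2–4 sample from the Week 12 by-visit value. Appendix 8 item 13a still grades the displaced sample.

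**2. Which tests are affected (Protocol Appendix 4, adult fasting scales).**

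- LDL: graded from 130 mg/dL.
- Total cholesterol: graded from 200 mg/dL.
- Triglycerides: no Grade 1; graded from 500 mg/dL (Grade 2).
- Fasting glucose, high: graded from 110 mg/dL.
- HDL: not graded, so only its change from baseline is lost.

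Lipids have no earlier scheduled study value. Glucose is in the Screening chemistry profile, so a Screening value known to be fasting could serve as baseline. Fasting is not required at Screening, however, and SAP 7.2.2.1 handles unknown status as nonfasting.

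**3. Possible size.** N = 565 (SAP Appendix 3, Safety Analysis Set). Neither document gives the share f dosed unfasted with a make-up draw on Day 2–4, or the share p of those with a graded value that pre-dates dosing. Both are assumptions: f from 1% to 10%, p from 10% to 50%.

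- Subjects without a fasting baseline = N × f: 565 × 0.01 = 5.65, about 6; 565 × 0.05 = 28.25, about 28; 565 × 0.10 = 56.5, about 57.
- Misclassified per graded test = N × f × p. Low: 565 × 0.01 × 0.10 = 0.565, about 0.6 (0.1 point). Middle: 565 × 0.05 × 0.30 = 8.475, about 8.5 (1.5 points). High: 565 × 0.10 × 0.50 = 28.25, about 28 (5 points).

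The points use 565 as denominator. The SAP's denominator is subjects with a post-baseline value for the test, which may be slightly smaller.

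**The case against.** The strongest reply is that permission for a visit to proceed says nothing about dosing, while 6.2.2 and footnote x are specific to Day 1 and put the procedures first. If those rules cover the fasting draw, the first dose waits for it, Study Day 1 moves with the dose, the make-up sample falls on or before it, and no baseline is lost. This stands. A reader might infer that the plan, followed as written, necessarily discards these baselines. The documents do not support that, because the loss occurs under only one of two unreconciled readings.

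A reader might also infer that the SAP can never use a make-up sample, or that every change-from-baseline analysis suffers. Neither follows: a same-day fasting draw qualifies, and CD4 count, creatinine, eGFR, liver tests and weight are unaffected.

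Nor is a biased treatment comparison shown. Assignment is randomized and blinded, so Day 1 fasting status should not differ systematically by arm, and no test is specified for the treatment-emergent tables. The p-values for change from baseline lose precision only.

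The fallback for a missing baseline is prespecified and conservative, and it is reasonable when nothing is known about the subject's starting value. It fits less well where a fasting sample drawn specifically to supply that value exists.

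Finally, the frequency is unknown. SAP 7.2.2.1 remarks that nonfasting glucose was not assessed at the baseline visit for most subjects. This suggests that it was for some, but gives no rate and no sign of a common problem.

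**Conclusion.** The point holds conditionally. Protocol 6.10.1 with footnote q and Protocol 6.2.2 with footnote x conflict for Day 1 and must be reconciled; this review does not say which should govern. For any subject dosed before a make-up draw on Study Day 2–4, the SAP's rules lead without exception to a missing fasting lipid baseline, usually a missing fasting glucose baseline, and treatment-emergent status for any graded fasting value, including the make-up sample.

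On the stated assumptions the size runs from negligible (about 6 subjects without baseline and 0.6 misclassified per test) to visible (about 57 and 28). It could be zero if no subject was dosed before the fasting draw.

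The effect is confined to secondary safety summaries, should be similar in both arms, and leaves the primary endpoint alone. It arises mainly in the randomized phase. The B/F/TAF group carries it into the all-B/F/TAF analysis, because Table 5 uses the same Day 1 cut-off. Subjects moving from DTG+F/TAF to open-label B/F/TAF normally have earlier blinded-phase fasting values that can supply their new baseline.

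**What to change.** 1. **Protocol.** Reconcile 6.10.1 and footnote q with 6.2.2 and footnote x, so that the order of the fasting draw and the first dose on Day 1 is stated once.
2. **SAP 7.2.2.1 and Appendix 8 item 13.** For a subject with no fasting value on or before Study Day 1, do not grade the Study Day 2–4 make-up sample as treatment-emergent. Use it as the reference grade for later fasting LDL, total cholesterol, triglycerides and glucose.
3. **SAP 7.2.3.** Keep the main change-from-baseline analysis on values from on or before Study Day 1. Add a sensitivity summary that takes the make-up sample as baseline, and report how many subjects it concerns.

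The make-up sample is deliberately not made the main baseline. It is drawn after dosing, and subjects coming from F/TDF change backbone on Day 1, where a post-dose baseline is hardest to defend.

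**Cost.** One derivation rule and one extra summary, with no new data. A few reference grades would come after up to 3 days of study drug. This SAP governs the final analysis and the Week 48 analysis has already been run, so final Week 48 treatment-emergent counts may differ slightly from those already produced. The study report should say so.

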# 6.10.2. Urine Samples

Urine samples will be collected for the following laboratory analyses:

- Urinalysis
- Urine pregnancy testing (Not collected at Screening and 30-day Follow-up Visits)

# 6.11. Virologic Failure

Virologic failure is defined as virologic rebound or having HIV-1 RNA  $\geq$  50 copies/mL at study drug discontinuation, or Week 48.

